7.4 LOFEXIDINE (LFX)

This medication was recently approved by the FDA for opioid detoxification and had been approved for the same purpose in the U.K. It is well-absorbed and reaches a peak plasma concentration 3-5 hours after a single dose. Administration with food does not alter its pharmacokinetics and about 30% of the dose is converted to inactive metabolites during the first pass. Its major metabolites do not influence or inhibit CYP450 isoforms except for a slight inhibition of CYP2D6, thus interactions with CYP substrates are not expected to be clinically significant. However, we are excluding strong or moderate inhibitors of CYP2D6 such as fluoxetine, paroxetine, or mirabegron, bupropion, quinidine, terbinafine, cimetidine, cinacalcet, duloxetine, and fluvoxamine. The major contributor to its metabolism is CYP2D6, though CYP1A2 and CYP2C19 may also be involved. The elimination half-life is about 12 hours. Nearly all of the oral dose is absorbed and accumulation can occur for up to 4 days with repeat dosing. Kidneys are the primary route of elimination, and unchanged drug accounts for 15-20% of the dose.

- **7.4.1 Safety**. Concomitant use of LFX may reduce the efficacy of oral naltrexone, therefore oral naltrexone cannot be given to patients in this study.
- **7.4.2 Methadone** and LFX both prolong the QT interval; therefore, methadone cannot be given to patients in this study.
- **7.4.3 Most common LFX AEs.** The most common AE's (≥10%) are orthostatic hypotension, bradycardia, hypotension, dizziness, somnolence, sedation and dry mouth. LFX can prolong the QT interval and potentiates the sedative effect of benzodiazepines, alcohol and other sedating drugs.
- **7.4.4 ECG and Vital Signs.** ECGs will be reviewed each day before administration of the first dose of study medication. Medication will be withheld if there is clinically significant QTc prolongation. Vital signs will be checked sitting and standing pre-dose and 1-2 hours post dose. Study medication will be withheld if the seated systolic BP is below 90 systolic or below 60 diastolic, and/or if the pulse is <50. A study physician will be contacted for dosing instructions if the seated systolic BP is >20 mm, or >10 mm diastolic below the last reading. Study medications may also be withheld or reduced if there is excessive sedation or other clinically significant AE's that may be caused by study medication. First degree AV block is common and does not indicate a serious problem. Study medication should be stopped and the study cardiologist contacted if there is 2nd degree heart block.

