7.1.3 Detoxification with Buprenorphine. Combining low and decreasing doses of buprenorphine with low and increasing doses of oral naltrexone was also studied as a way to transition to naltrexone and the results were positive in an early study where 56% in the experimental group transitioned to XR-NTX vs 33% in the buprenorphine group (Sullivan et al, 2017). However, a larger trial of 378 patients randomized to one of three regimens: NTX + BUP; NTX + placebo BUP (PBO-B); placebo NTX (PBO-N) + PBO-B found no difference in transition to XR-NTX across groups (41-46%), although for those inducted onto XR-NTX, the management of opioid withdrawal symptoms prior to starting XR-NTX was achieved in a structured outpatient setting using a well-tolerated, fixed-dose ancillary medication regimen common to all three groups. (Bisaga et al, 2018).

7.1.4 Detoxification with Pregabalin. During the time that PGB was available without a prescription in Russia, clinicians observed that opioid addicted patients were using it to suppress withdrawal when their heroin supply ran out. These observations led to a study in which 34 heroin-addicted patients were randomized to detoxification protocols using PGB alone, or clonidine alone (Krupitsky et al, 2017). While groups did not differ on baseline clinical or demographic features, 15 of the 19 PGB subjects completed treatment (79%) compared to 7 of 15 (47%) in the clonidine group (p = 0.05, Fisher exact test), and a Kaplan-Meier Survival Analysis confirmed better retention in the PGB group (p = .001). There was no significant group difference in reduced severity of withdrawal, however the pregabalin group reported less opioid craving (p= .05), less anxiety (p=0.05), less depression (p=0.05), and higher assessments of general health (p < 0.05). Ketorolac was available as needed for pain, and the average dose of symptom-triggered ketorolac in the clonidine group was almost twice that of the PGB group (60.5 \pm 8.2mg vs. 36 \pm 7.8mg, (p< 0.05). In addition, the PGB group reported less fatigue compared to the clonidine group (16% vs. 47%, p < 0.05) and there was no significant difference in AR's between groups. These findings were consistent with studies using rodent models that demonstrated PGB attenuates opioid withdrawal (Vashchinkina et al 2017).

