7.3.2 DOSING SCHEDULES

Table 2: LFX Dosing: all tablets are 0.18 mg

	Time	Day 1	Day 2	Day 3	Day 4	Day 5	Day 6	Day 7
All	0800	0.00	0.54	0.54	0.54	0.54	0.36	0.18
Groups								
	1200	0.54	0.54	0.54	0.54	0.36	0.18	0.18
	1600	0.54	0.54	0.54	0.54	0.36	0.18	0.18
	2000	0.54	0.54	0.54	0.54	0.36	0.18	0.18
	Total	1.62	2.16	2.16	2.16	1.62	0.90	0.72

Table 3: PGB and PGB-PLA Dosing (in mg)

	Time	Day 1	Day 2	Day 3	Day 4	Day 5	Day 6	Day 7
Group 1	0800	0	200	200	200	100	50	25
(PGB)	1200	100	100	100	100	75	25	25
	1600	100	100	100	100	75	25	25
	2000	200	200	200	200	150	100	25
	Total	400	600	600	600	400	200	100
Group 2	0800	0	PLAC	PLAC	PLAC	PLAC	PLAC	PLAC
(PGB-PLA)	1200	PLAC						
	1600	PLAC						
	2000	PLAC						
	Total	0	0	0	0	0	0	0

7.3.3 Dosing Guidelines:

As stated below investigators may choose to stop or reduce the dose of either Study Medication although BP and pulse changes are more likely to be due to lofexidine and sedation due to pregabalin.

- Patients can be started and continued on Study Medication if the pulse is 50 or above. Medication should be held if the pulse is <50.
- Patients can be started on Study Medications on Day 1 if COWS >/=6 and SOWS_>/= 4
- A study physician is required to hold the dose of Study Medication if the systolic BP is < 90 and/or the diastolic is <60. Investigators should hold both lofexidine and pregabalin until the next dosing time when they can be restarted if the vitals return to 90/60 or above.
- Hypotension is a potential side effect of lofexidine; sedation, dizziness, or light-headedness are
 potential side effect of pregabalin. A drop of 20 mm or more systolic and/or 10 mm or more diastolic;
 or significant lightheadedness or dizziness, are grounds for holding or reducing a dose of the
 medication that is the most likely cause. Investigators should use their judgement on which Study
 Medication to hold or reduce and by how much.
- **7.3.3.1** The following procedures will minimize risks associated with transient vs. persistent BP changes:
 - If the BP reading shows a pre-medication sitting and/or standing drop (orthostatic change) of more than 20mm systolic, and/or more than 10 mm diastolic, wait 2-3 minutes and repeat the sitting and standing BP.

- If the repeat readings are within the acceptable range as defined by the protocol, dosing can be continued as planned.

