13.0 STATISTICAL PLAN

13.1 DATA ANALYSES

[name], the CSA Statistician, and his staff will perform data analyses. Prior to analyses, standard data screening/cleaning procedures will be applied. These procedures will screen the data for data-entry errors, check for outliers, assess the extent and pattern of missing data, and check that appropriate assumptions of normality are met whenever necessary.

13.2 **SAMPLE SIZE DETERMINATION**

Power Analyses: The primary goal of this study is to determine if the PBG/LFX combination versus LFX/PGB-PLA is safe and effective in OUD individuals, and shows a reduction in opioid–related withdrawal effects greater than lofexidine alone. To assist in this determination, we provide power for the primary comparison of longitudinal subjective withdrawal measures, comparing the groups on rate of decrease across days, using a linear group by time effect for the mixed effects models described above. We have one primary outcome, so use an alpha level of 0.05, and we use two- sided tests. 90 subjects, approximately 30 from each of three sites (MMTC and PENN might have more than 30), who will be randomized into two groups, with 30 assigned to LFX/PGB-PLA, and 60 to LFX plus a starting daily dose of 400 mg of PGB and increasing to 600mg PGB on day 2. Assuming an overall dropout rate of 40%, and within-subjects' correlations of 0.5, the methods of Hedeker et al (Hedeker, Gibbons and Waternaux, 1999) show that this provides 80% power for a group by linear time interaction effect of Cohen's d=0.44 standard deviations between the two groups.

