13.3 STATISTICAL METHODS

13.3.1 Primary Outcome - Reduction in SOWS-Gossop criterion. The primary outcome will be reduction in subjective withdrawal as measured by the SOWS - Gossop (scores range from zero to 30). The groups will be compared on the 14 repeated SOWS-Gossop responses obtained during the seven-day detoxification period, using linear mixed-effects regression models; the SOWS-Gossop total will be regressed on a three-level factor for site, and a two-level factor for medication group, with time and group by time effects. The covariance structure will include a random intercept and correlated residuals, with a random slope included if necessary for fit. Contrasts between the PGB group and the PGB-PLA group will be estimated from the model. Exploratory analyses of heterogeneity of dose effects across sites will be performed including a site by dose interaction term in the main model.

These models will provide valid estimates and tests if any missing data is statistically ignorable (Laird, 1998). Dropout may be associated with reports of subjective withdrawal, and will be ignorable if available subjective scores prior to dropout are predictive of dropout. To assess possible effects of non-ignorability on inference, we will perform sensitivity analyses using pattern- mixture models and selection models. For pattern mixture models, subjects are grouped on the basis of their pattern of missing data. Usually, rarely occurring patterns are grouped, so as to keep the number of pattern-groups at a manageable level. This grouping defines a nominal variable, which is then used as a predictor in the analyses, although a covariate representing missingness on a continuous scale can also be used. The regression coefficients associated with this variable, and its interactions with the other predictors, quantify how response-predictor relationships differ across the different patterns of missingness. Overall predictor effects may be found by averaging over the patterns (Little, 1993). For longitudinal data, subjects are usually stratified according to the visit after which they dropped out. Hedeker and Gibbons (1997), and Hedeker and Rose (2000), apply these methods to mixed effects models in longitudinal data. Selection models (Little, 1995; Kenward, 1998; Verbeke and Molenberghs, 2000) take a different approach, by explicitly modeling the probability of drop out, and incorporating the predicted probabilities

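### If the common SOWS course bends and dropout differs by arm, the linear-time slope test is biased with no drug effect, in a direction that cannot be known in advance

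*Combined protocol and SAP*

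**What the plan says.** Section 13.2 describes the primary comparison as "comparing the groups on rate of decrease across days, using a linear group by time effect for the mixed effects models described above". It sets "We have one primary outcome, so use an alpha level of 0.05, and we use two- sided tests", with patients "who will be randomized into two groups, with 30 assigned to LFX/PGB-PLA, and 60 to LFX", and continues: "Assuming an overall dropout rate of 40%, and within-subjects' correlations of 0.5". The stated result is 80% power for d = 0.44.

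Section 13.3.1 analyses 14 SOWS readings over seven days, with site, group, time and group-by-time terms, a random intercept, correlated residuals and a random slope if needed. It does not say whether time is linear or categorical; the optional random slope points to continuous time. The statistical paragraph of Section 3.0 lists no time term. On missing data, 13.3.1 states: "These models will provide valid estimates and tests if any missing data is statistically ignorable". It adds pattern-mixture and selection models as sensitivity analyses.

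On the likely course of SOWS:
- Section 7.4: "Nearly all of the oral dose is absorbed and accumulation can occur for up to 4 days with repeat dosing".
- Section 7.3.2 ("Table 2: LFX Dosing: all tablets are 0.18 mg"): scheduled daily totals in both arms are 1.62, 2.16, 2.16, 2.16, 1.62, 0.90 and 0.72 mg. Section 3.0 lets doses be reduced or withheld on Days 1 to 7.
- Section 9.1.2: dosing may start at SOWS 4 on a 0 to 30 scale. Section 8.2 counts a score under 6 as part of a successful detoxification.

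On retention, Section 7.1.4 reports from an earlier trial of pregabalin alone against clonidine alone: "15 of the 19 PGB subjects completed treatment (79%) compared to 7 of 15 (47%) in the clonidine group". That trial found no significant group difference in withdrawal severity.

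**The concern.** A straight line fitted to a bent curve depends on which part of the curve is observed. A patient who leaves on Day 3 contributes only the early part; a completer contributes all of it. If one arm loses more patients early, its fitted line is set more by the early days, and the two lines differ although both arms follow the same true curve. Ignorable dropout does not cure this, because likelihood methods also need the mean model to be right. The statement in 13.3.1 gives only the first of these two conditions.

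At stake is the error rate of the single primary test. Unequal retention is foreseeable, since better completion on the combination is itself a secondary objective (Section 8.2). Sections 13.4.2 (POSS) and 13.5.3 (ISI) reuse similar models.

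**Working it through.** **Inputs from the documents.** 60 v 30 patients, 14 readings, within-subject correlation 0.5, two-sided 0.05, d = 0.44, 40% overall dropout.

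**Assumptions.** The documents give no SOWS time course, no SOWS SD and no dropout by arm. I assume total SD 1, compound symmetry, readings on Days 2 to 7 at 08:00 and 16:00 (the times that Section 9.1.2 gives for the craving scale), and dropout at random within arm, spread evenly over the intervals between readings. Dropout of 21% v 53% is 100 − 79 and 100 − 47 from the earlier trial. Curves are piecewise linear and identical in both arms.

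**Step 1: the plan's own figure.** With 40% dropout in each arm, the standard error of the group-by-linear-time coefficient, scaled to the whole week, is 0.156. Power = Φ(0.44/0.156 − 1.96) = Φ(0.86) = 80%. The stated power is reproduced. Other spacings and dropout timings give 77.0% to 82.4%.

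**Step 2: expected estimate with no drug effect.** The expected coefficient is the last element of (Σ XᵀV⁻¹X)⁻¹ Σ XᵀV⁻¹μ, summed over arms and dropout patterns, where X holds intercept, time, group and group × time, and μ is the common curve. The chance of a significant result in the favoured tail is Φ(|b|/SE − 1.96). With 21% v 53% dropout, SE = 0.160. Negative values favour pregabalin.

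| Common SOWS course | Bias b (SD over the week) | Null trials in the favoured tail (nominal 2.5%) |
|---|---|---|
| Straight fall of 1 SD | 0.000 | 2.5% each side |
| Rise 0.3, then fall to 0.5 below start | −0.052 | 5%, pregabalin better |
| Rise 0.5, then fall to 0.8 below | −0.086 | 8%, pregabalin better |
| Rise 0.7, then fall to 1.2 below | −0.124 | 12%, pregabalin better |
| Flat to Day 4, then fall 1 | −0.064 | 6%, pregabalin better |
| Fall 1 by Day 4, then plateau | +0.067 | 6%, pregabalin worse |
| Fall 1 by Day 4, then 50% rebound | +0.099 | 9%, pregabalin worse |

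The rising curves peak 1.75 days after the first dose. For example, Φ(0.086/0.160 − 1.96) = Φ(−1.42) = 8%. Moving the peak to 2 days gives −0.135 and 13% for the largest curve.

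**Step 3: other dropout splits.**
- 21% v 53% averages (60 × 21 + 30 × 53)/90 = 31.7%. A split of 30.5% v 59% averages (60 × 30.5 + 30 × 59)/90 = 40%, the plan's figure, and gives −0.055, −0.090 and −0.129 for the three rising curves.
- If pregabalin loses more (47% v 26%), the signs reverse: +0.055 for the middle rising curve, −0.043 for the plateau, −0.063 for the rebound.
- With 40% in each arm the bias is zero for every shape.

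**Step 4: simulation.** With 1,500 simulated null trials per scenario, the three rise-then-fall sizes gave bias of about −0.05, −0.08 and −0.14 SD, and pregabalin declared better in 4–5%, 5–6% and 10%. When dropout at 53% v 21% depended on the last score, the bias was −0.05 to −0.11 SD and the rate 4.5–7.0%.

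**Step 5: the remedy.** Replacing the common straight line with 14 reading-specific means, with group and group × linear time kept, gives zero expected bias for every shape and split above. The standard error is unchanged to three decimals (0.160 v 0.160). In simulation the bias was within 0.005 SD and the one-sided rate 2.2–2.8%.

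**The case against.** A reader might infer that the plan leans towards pregabalin, since the earlier trial suggests better retention on it. The documents do not support a direction. Lofexidine build-up followed by taper would, on its own, predict SOWS falling and then flattening or rebounding; with better retention on pregabalin that biases the test against pregabalin. The bias favours pregabalin only if SOWS first rises or stays flat, which a start at SOWS 4 makes plausible but does not establish. Nor is better retention assured. The 79% v 47% comes from 34 patients on pregabalin alone or clonidine alone, and Section 7.3.6 reports more discontinuations for adverse events on pregabalin than on placebo (14% v 7%).

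It would also go too far to say that SOWS cannot be linear, or that every patient follows the scheduled profile. The accumulation statement concerns drug level and says only that it can occur, and holds and reductions are allowed. Linear time is explicit only in 13.2; 13.3.1 leaves the form open.

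The best defence is the planned pattern-mixture analysis. Within one dropout pattern both arms see the same stretch of curve. Even a crude completer/dropout split with pooled weights cuts the bias for rise-then-fall curves (peak at 1.5 days, constant dropout hazard) from −0.045, −0.075 and −0.107 to −0.010, −0.017 and −0.024 SD. That stands, but it is a sensitivity analysis for non-ignorable dropout and does not replace the primary test.

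**Conclusion.** The concern holds, without a direction. The powered test is a linear slope contrast and no term is planned for a bent common course. Such a course together with unequal dropout gives a false slope difference under ignorable dropout, which can create a false positive or mask a real effect. The size is modest: about 0.05 to 0.14 SD, or 11% to 32% of the planned 0.44 (0.05/0.44 and 0.14/0.44), with about 5% to 13% of null trials in one tail instead of 2.5%. These figures rest on assumed curves and an assumed dropout split borrowed from a different comparison. A truly straight course or equal dropout removes the problem. The stated 80% power is not in dispute.

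**What to change.** In 13.3.1, state that the common time trend is a 14-level factor, one mean per scheduled SOWS reading, shared by both arms, and that the group-by-linear-time coefficient remains the powered primary test. Amend the validity statement to say that it also requires a correctly specified mean over time. Use one mean per scheduled reading where 13.4.2 and 13.5.3 reuse the model.

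The cost is 14 − 2 = 12 extra fixed-effect parameters on up to 90 × 14 = 1,260 readings, with negligible loss of precision and no new data or patients. The change protects the test when there is no drug effect. If pregabalin's own effect is not linear in time, the coefficient is still only an average slope and should be reported as such.

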- **7.5.6** XR-NTX and Renal Impairment. A pharmacokinetic analysis indicated that mild renal insufficiency (creatinine clearance of 50-80 mL/min) had little or no influence on XR-NTX pharmacokinetics and that no dosage adjustment is necessary. Pharmacokinetics of XR-NTX have not been evaluated in subjects with severe renal insufficiency, thus individuals with severe renal abnormalities will not be included in this study.
- **7.5.7 XR-NTX and Gender.** In a study of healthy subjects (n=18 females; 18 males), gender did not influence the pharmacokinetics of XR-NTX.
- **7.5.8 XR-NTX and Drug-Drug Interactions.** Studies evaluating drug-drug interactions have not been performed.
- **7.5.9** XR-NTX and Reversal of Blockade for Pain Management. In an emergency situation, suggestions for pain management are regional anesthesia or non-opioid analgesics. If opioids are required, they must be provided in a setting where establishment and maintenance of a patent airway and assisted ventilation are readily available from persons trained in the use of anesthetic drugs and management of respiratory depression.

- **7.5.10** Depression and Suicidality. In controlled trials among patients with alcohol dependence, AEs of a suicidal nature (ideation, attempts and completed suicides) were infrequent, but more common in patients treated with XR-NTX than placebo (1%). In some cases, suicidal thoughts or behaviors occurred after study discontinuation but in the context of an episode of depression that began while the patient was on the medication. Two completed suicides occurred in alcohol treatment studies, both in patients treated with XR-NTX, and depression-related events were more common in patients treated with XR-NTX than in those on placebo (1%). However, two studies that have specifically examined the relationship between depression and XR-NTX treatment found that depression and anxiety decrease in association with detoxification and naltrexone treatment (Mysels et al, 2011; Krupitsky et al, 2016)
- **7.5.11** Naltrexone Contraindications. Patients should not receive XR-NTX if they are taking opioid analgesics; have current opioid dependence; are in opioid withdrawal; failed a naloxone challenge or have a positive urine screen for opioids; exhibited hypersensitivity to naltrexone, PLG, carboxymethylcellulose, or any other components of the diluent; or have acute hepatitis or liver failure.
- 7.5.12 Opioid Overdose Following an Attempt to Overcome the XR-NTX Blockade.

 Patients will be told that attempting to overcome the blockade by administering large doses of opioids may result in fatal overdose.
- **7.5.13** Eosinophilic Pneumonia. There was one diagnosed, and one suspected case of eosinophilic pneumonia in clinical trials. Both required hospitalization and resolved with antibiotics and corticosteroids. Should a person receiving Vivitrol ® develop dyspnea and hypoxemia this diagnosis should be considered.
- 7.5.14 Data from the Russian XR-NTX Study of Opioid Dependent Patients: [name] provided the following data from the study that led to FDA approval of XR-NTX for opioid dependence (Krupitsky et al, 2011). In that study, 6 of the 126 subjects (4.8%) randomized to 380 mg XR-NTX reported injection site pain as compared to one of 124 subjects (0.8%) assigned to XR-NTX placebo. ALT in the 380 mg XR-NTX group increased an average of 6.9 IU/L as compared to an increase of 5.6 IU/L in the XR-NTX placebo group; AST increased 3.8 IU/L in the XR-NTX 380 mg group, and 6.7 IU/L in the XR-NTX placebo group; 63 of the 126 (50%) subjects in the XR-NTX 380 mg group reported an AE as compared to 40 of 124 (32%) in the placebo group. Three patients reported 4 SAEs in the XR-NTX 380 mg group (AIDS/HIV or infections); and 4 reported 5 SAEs in the placebo group (2 infections, 1 psychotic disorder, 1 other drug dependence, 1 peptic ulcer). These data suggest that the risks associated with XR-NTX among persons with opioid dependence are no different or more common that those seen among alcoholics.

